STUDY PROTOCOL COVER PAGE

Official Title: Randomised Controlled Trial of Two Different Cumulative Dosages of Roaccutane for Cystic Acne

Short Title: Roaccutane 120 mg/kg vs 150 mg/kg for Cystic Acne

Principal Investigator: [name], St George Hospital, Kogarah NSW, Australia

Study Identifier (NCT Number): To be assigned by ClinicalTrials.gov upon registration

Date: 23 June 2005

PROTOCOL

RANDOMISED CONTROLLED TRIAL OF TWO DIFFERENT CUMULATIVE DOSAGES OF ROACCUTANE FOR CYSTIC ACNE

Objective: Comparison of the effectiveness of Roaccutane at total cumulative dosages of 120 mg/kg vs 150 mg/kg.

Clinical Hypothesis: A 150 mg/kg cumulative dosage regimen is more effective at treating acne vulgaris and the presence of a remission from the disorder than 120 mg/kg.

Methodology: The study will be a multicenter, controlled, randomized study.

Number of subjects: It has been determined that to detect a 10% difference between the two dosage schedules of Roaccutane which are being tested (120mg/kg vs 150mg/kg) 450 subjects will be required with 225 in each group.

Diagnosis and Main Inclusion Criteria: Male or Female subjects, of any age, of any race, with a clinical diagnosis of nodulo-cystic acne as well as patients who have been unresponsive to standard acne vulgaris treatments.

Exclusion Criteria: pregnant or lactating female patients, female patients with polycystic ovarian syndrome, insulin resistance syndrome, previous use of Roaccutane, patients with congenital adrenal hyperplasia, patients with any internal malignancy (excluding skin cancer); females of reproductive potential who refuse to take the oral contraceptive pill to take roaccutane; patients who in the investigator's opinion would be unlikely to be compliant.

Investigational Product: Roaccutane 20mg tablets 150mg/kg total dose.

Comparator Product: Roaccutane 20mg tablets 120mg/kg total dose

Study Duration/Visits: Visits include before treatment initiation, and at least every two months thereafter, including when the 120mg/kg dose and at 150mg/kg cumulative doses are reached. The patients are assessed 3 months after finishing roaccutane and at one year after roaccutane treatment has ceased to record response and recurrence rates.

Criteria for Evaluation: Acne lesion counts will consist of counting specifically white heads, blackheads, papules, pustules, nodules, deep pustules measured on both the left and right sides of the face, the same lesions will be measured on the chest and on the back. Scarring assessments will be done in terms of icepick scars, macular atrophic scars, follicular macular atrophic scars, hypertrophic/keloid scars and peri-follicular papular scars on the face, chest and back. An acne grade will also be assigned which ranges from 1 - 8. This acne grade has been established in the article "*Predictive*

factors for failure of isotretinoin treatment in acne patients; results from a cohort of 237 patients", Dermatology 1999;198: 278-283.

Other methods of note:

[figure not shown]
1. For consistency, all female patients of child bearing potential will be asked to use an oral contraceptive pill. A second form of contraception will be required.
2. Standard investigations for this study to identify potential factors include two negative serum pregnancy tests immediately before starting on treatment, testosterone level, sex hormone binding globulin, luteinizing hormone level, follicle stimulating hormone level, androstenedione level, 17 hydroxy-progesterone level and glucose tolerance tests. Transabdominal and/or transvaginal ovarian ultrasound when appropriate.
3. Other laboratory tests will be drawn before starting roaccutane including a full blood count, UEC, lipid panel, and liver function tests.
4. Once the decision to start Roaccutane has been taken, patients will be randomised to either treatment group that being 120mg/kg or 150mg/kg cumulative dose. If the patient's acne is still active during the month they are due to cease treatment their course of treatment will be continued.
5. Before commencing on either Roaccutane dose a study consent form, which has been approved by the SESIAHS Ethics Committee,
6. Separate forms are available for minors.

NAME OF THE DRUG

ROACCUTANE

(isotretinoin)

CAS 4759-48-2

13-cis-Retinoic Acid

Chemically, isotretinoin is (2Z, 4E, 6E, 8E)-3,7-dimethyl-9-(2,6,6-trimethylcyclohex-1-enyl)nona-2,4,6,8-tetraenoic acid and is also known as 13-cis-retinoic acid. Isotretinoin is related to both retinoic acid and retinol (vitamin A). The molecular formula is C₂₀H₂₈O₂. Isotretinoin has a molecular weight of 300.44.

DESCRIPTION

Isotretinoin is a yellow orange to orange crystalline powder, practically insoluble in water, soluble in methylene chloride, sparingly soluble in ether and slightly soluble in alcohol. It is sensitive to air, heat and light, especially in solution.

ROACCUTANE is available in 10 and 20 mg soft gelatin capsules for oral administration. In addition to isotretinoin, the capsules contain soya oil, yellow beeswax, hydrogenated vegetable oil and hydrogenated soya oil.

The capsule shell contains gelatin, glycerol, purified water, titanium dioxide, canthaxanthin CI40850 and proprietary ingredient Karion 83 (by R.P. Scherer GmbH, ARTG No. 2072).

The printing ink, black ink edible A-R-10379 (ARTG No. 2268) contains shellac and iron oxide black CI77499.

PHARMACOLOGY

Pharmacodynamics

Isotretinoin is a retinoid that inhibits sebaceous gland function and keratinisation. The exact mechanism of action of ROACCUTANE is unknown.

Clinical improvement in cystic acne patients occurs in association with a reduction in sebum secretion. The decrease in sebum secretion is reversible and the extent is related to the dose and duration of treatment with ROACCUTANE and reflects a reduction in sebaceous gland size and an inhibition of sebaceous gland differentiation.

Pharmacokinetics

Absorption

There is considerable inter-individual variation in the bioavailability of oral isotretinoin. After oral administration of 80 mg (2 x 40 mg capsules) given in the fasting state peak plasma concentrations ranged from 167 to 459 nanogram/mL and mean time to peak was 3.2 hours in healthy volunteers, while in acne patients peak concentrations ranged from 98 to 535 nanogram/mL (mean 262 nanogram/mL) with a mean time to peak of 2.9 hours.

The bioavailability of ROACCUTANE capsules taken with food is 1½ to 2 times greater than when taken in a fasting state.

Distribution

Tissue Distribution in Animals: Tissue distribution of ^{14}C - isotretinoin in rats revealed high concentrations of radioactivity in many tissues after 15 minutes, with a maximum in 1 hour, and declining to non-detectable levels by 24 hours in most tissues. After seven days, however, low levels of radioactivity were detected in the liver, ureter, adrenal, ovary and lacrimal gland.

The drug is 99.9% bound in human plasma almost exclusively to albumin.

Metabolism

The major identified metabolite in blood and urine is 4-oxo-isotretinoin. Tretinoin and 4-oxo-tretinoin were also observed. After two 40 mg capsules of isotretinoin, maximum concentrations of the metabolite of 87 to 399 nanogram/mL occurred at 6 to 20 hours. The blood concentration of the major metabolite generally exceeded that of isotretinoin after 6 hours.

The mean \pm SD minimum steady-state blood concentrations of isotretinoin were 160 \pm 19 nanogram/mL in 10 patients receiving 40 mg twice daily. After single and multiple doses, the mean ratio of areas under the curves of isotretinoin to 4-oxo-isotretinoin is 3 to 3.5.

Excretion

The terminal elimination half-life of isotretinoin ranged from 10 to 20 hours in volunteers and patients. Following an 80 mg liquid suspension oral dose of ^{14}C -isotretinoin, ^{14}C -activity in blood declined with a half-life of 90 hours. Relatively equal amounts of radioactivity were recovered in the urine and faeces with 65-83% of the dose recovered. The apparent half-life for elimination of the 4-oxo-metabolite ranged from 11 to 50 hours with a mean of 29 hours. This metabolite is subject to recycling in the enterohepatic circulation.

INDICATIONS

ROACCUTANE is indicated for the treatment of severe cystic acne, and a single course of therapy has been shown to result in complete and prolonged remission of disease in many patients. If a second course of therapy is needed, it should not be initiated until at least eight weeks after completion of the first course, since experience has shown that patients may continue to improve while off drug. Because of significant adverse effects associated with its use, ROACCUTANE should be reserved for patients with severe cystic acne who are unresponsive to conventional therapy, including systemic antibiotics.

CONTRAINdications

Use in Pregnancy (Category X): ROACCUTANE must not be used by females who are pregnant or who may possibly become pregnant while undergoing treatment.

Major human fetal abnormalities related to ROACCUTANE administration have been reported, including hydrocephalus, microcephalus, abnormalities of the external ear (micropinna, small or absent external auditory canals), eye abnormalities (including microphthalmia), cardiovascular abnormalities, facial dysmorphia, cleft palate, thymus gland abnormality, parathyroid gland abnormalities and cerebellar malformation.

Women of childbearing potential should not be given ROACCUTANE until pregnancy is excluded. It is strongly recommended that a pregnancy test be performed within two weeks prior to ROACCUTANE therapy. ROACCUTANE therapy should start on the second or third day of the next normal menstrual period. An effective form of contraception should be used for at least one month before and also throughout ROACCUTANE therapy.

It is recommended that contraception be continued for one month following discontinuation of ROACCUTANE therapy. Females should be fully counseled on the serious risk to the fetus should they become pregnant while undergoing treatment. If pregnancy does occur during treatment, the physician and patient should discuss the desirability of continuing the pregnancy.

ROACCUTANE is contraindicated in patients who are breast- feeding (see PRECAUTIONS – USE IN LACTATION).

ROACCUTANE is contraindicated in patients with severely impaired liver function and in patients with chronic abnormally elevated blood lipid values.

ROACCUTANE is also contraindicated in people who are hypersensitive to the drug or other ingredients in ROACCUTANE capsules or to other retinoids.

ROACCUTANE is contraindicated in patients who have pre-existing hypervitaminosis A.

Rare cases of benign intracranial hypertension have been reported after ROACCUTANE and after tetracyclines. Concomitant treatment with tetracyclines is therefore contraindicated. (See also PRECAUTIONS: Interactions with Other Drugs).

PRECAUTIONS

Information for patients

Women of childbearing potential should be warned that the drug causes birth defects. They should be instructed that they must not be pregnant when ROACCUTANE therapy is initiated, and that they should use an effective form of contraception while taking ROACCUTANE and for one month after ROACCUTANE has been stopped. (See CONTRAINDICATIONS).

Patients should be informed that transient exacerbation of acne has been seen, generally during the initial period of therapy.

Because of the relationship of ROACCUTANE to Vitamin A, patients should be advised against taking vitamin supplements containing Vitamin A to avoid additive toxic effects.

Donation of blood by patients during and within one month of cessation of ROACCUTANE treatment to women of childbearing potential should be avoided.

Wax epilation should be avoided in patients on ROACCUTANE and for a period of 5-6 months after treatment because of risk of scarring or dermatitis.

Dermabrasion should be avoided in patients on ROACCUTANE and for a period of 5-6 months after treatment because of risk of hypertrophic scarring in atypical areas.

Pseudotumour cerebri

ROACCUTANE use has been associated with a number of cases of pseudotumour cerebri (benign intracranial hypertension), some of which involved the concomitant use of tetracyclines. Early signs and symptoms of pseudotumour cerebri include papilloedema, headache, nausea and vomiting, and visual disturbances. Patients with these symptoms should be screened for papilloedema and, if present, they should be told to discontinue ROACCUTANE immediately and be referred to a neurologist for further diagnosis and care.

Visual Abnormalities

Corneal opacities have occurred in patients receiving ROACCUTANE for acne and more frequently when higher drug dosages were used in patients with disorders of keratinisation. All ROACCUTANE patients experiencing visual difficulties should discontinue the drug and have an ophthalmological examination.

A number of cases of decreased night vision have occurred during ROACCUTANE therapy. As the onset in some patients was sudden, patients should be advised of this potential problem and warned to be cautious when driving or operating any vehicle at night.

Dry eyes, corneal opacities, conjunctivitis, blepharitis, intolerance to contact lenses, decreased night vision and keratitis usually resolve after discontinuation of therapy. Due to the possible occurrence of keratitis, patients with dry eyes should be monitored. Patients experiencing visual difficulties should be referred for an expert ophthalmological examination and withdrawal of ROACCUTANE considered.

Biochemical Abnormalities

Rises in alanine and aspartate aminotransferase enzymes (ALT and AST) have been reported. Liver function tests, especially AST and blood lipids should be measured before therapy and at monthly intervals during therapy and at the end of treatment. When transaminase levels exceed the normal levels, reduction of the dose or discontinuation of treatment may be necessary.

Isotretinoin causes elevation of serum triglycerides and cholesterol as well as a decrease in H.D.L., which appear to be related to duration of treatment and are reversible on cessation of treatment. The degree of elevation may also be dose dependent although this has not been conclusively established.

At doses of greater than 1 mg/kg/day, approximately one in four patients has been found to develop elevated triglycerides while taking ROACCUTANE. At lower doses triglyceride levels elevated above the normal range are uncommon.

Acute pancreatitis, which is potentially fatal, sometimes associated with serum triglycerides levels $>8\text{g/L}$, has been reported. Hence, ROACCUTANE should be discontinued if uncontrolled hypertriglyceridemia or symptoms of pancreatitis occur.

Predisposing factors such as a family history of lipid disorders, obesity, alcohol abuse, diabetes and smoking should be assessed. Serum lipid should be determined prior to therapy and again after about 4 weeks, and subsequently at three month intervals unless more frequent monitoring is clinically indicated.

Some patients have been able to reverse triglyceride elevations by weight reduction and restriction of dietary fat and alcohol while continuing to take ROACCUTANE. Serum lipid values usually return to normal on reduction of the dose or discontinuation of treatment.

In high risk patients (with diabetes, obesity, alcoholism or lipid metabolism disorder) undergoing treatment with ROACCUTANE, more frequent checks of serum values for lipids and/or blood glucose may be necessary.

Hyperostosis

In clinical trials of disorders of keratinisation with a mean dose of 2.24 mg/kg/day a high prevalence of skeletal hyperostosis was noted. Bone changes including premature epiphyseal closure have occurred after administration of high doses for long periods for treating disorders of keratinisation.

Minimal skeletal hyperostosis has also been observed by X-rays in prospective studies of nodular acne patients treated with a single course of therapy at recommended doses.

Due to the possible occurrence of these bone changes, a careful evaluation of the risk/benefit ratio should be carried out in every patient and ROACCUTANE administration should be restricted to severe cases.

Hepatotoxicity

Several cases of clinical hepatitis have been noted which are considered to be possibly or probably related to ROACCUTANE therapy. Additionally, mild to moderate elevations of liver enzymes have been observed in approximately 15% of individuals treated during clinical trials, some of which normalised with dosage reduction or continued administration of the drug. If normalisation does not readily occur or if hepatitis is suspected during treatment with ROACCUTANE, the drug should be discontinued and the etiology further investigated.

Psychiatric disorders

Depression, psychosis and, rarely, suicidal ideation and attempts have been reported with ROACCUTANE. Particular care needs to be taken in patients with a history of depression and all patients should be monitored for signs of depression. Although no mechanism of action for these events has been established, discontinuation of therapy may be insufficient and further evaluation by a psychiatrist may be necessary.

Inflammatory bowel disease

ROACCUTANE has been associated with inflammatory bowel disease (including regional ileitis) in patients without a prior history of intestinal disorders. Patients experiencing abdominal pain, rectal bleeding or severe (hemorrhagic) diarrhea should discontinue ROACCUTANE immediately.

Anaphylactic reactions

These have been reported rarely and only after previous topical exposure to retinoids. Allergic cutaneous reactions are reported infrequently. Serious cases of allergic vasculitis, often with purpura (bruises and red patches) of the extremities and extracutaneous involvement have been reported. Severe allergic reactions necessitate interruption of therapy and careful monitoring.

Renal Impairment

ROACCUTANE should be started at a lower dose in patients with severe renal insufficiency and afterwards dose adjusted according to tolerance.

Exercise Tolerance

Myalgia and arthralgia may occur and may be associated with reduced tolerance to vigorous exercise (see **Adverse Reactions**). Isolated instances of raised CPK levels have been reported in patients receiving ROACCUTANE, particularly those undergoing vigorous physical activity.

Carcinogenesis, Mutagenesis and Impairment of Fertility

In Fischer 344 rats given isotretinoin at dosages of 32 or 8 mg/kg/day for greater than 18 months, there was dose-related increased incidence of pheochromocytoma. The incidence of adrenal medullary hyperplasia was also increased at the higher dosage. There is doubt as to the validity of this animal model as a predictor of tumorigenicity in man, as the Fischer rat is genetically predisposed to the Multiple Endocrine Neoplasia Syndrome which includes spontaneous occurrence of pheochromocytoma. In these studies there was also a dose-related decrease in the incidence of liver adenomata, liver angioma and leukemia.

Isotretinoin was negative in tests for gene mutation (histidine reversion in *S. typhimurium*), chromosomal damage *in vitro* (Chinese hamster lung cell and *S. cervisiae* D7 assays) and *in vivo* (Mouse micronucleus test), and unscheduled DNA synthesis *in vitro* (rat hepatocytes).

In the reproductive studies in rats (2, 8 or 32 mg/kg/day; 2-generation), no adverse effects were noted on gonadal function, fertility, gestation or neonatal viability, although the average weight in the high dose group was slightly reduced.

In dogs, testicular atrophy was noted after treatment with isotretinoin for approximately 30 weeks at dosages of 60 or 20 mg/kg/day. In general, there was microscopic evidence for appreciable depression of spermatogenesis but some sperm were observed in all testes examined and in no instance were completely atrophic tubules seen. In studies in 66 human males, 30 of who were patients with cystic acne, no significant changes were noted in the count or motility of spermatozoa in the ejaculate.

Use in Pregnancy

Pregnancy Category X

Isotretinoin is a known human teratogen and should not under any circumstances be administered during pregnancy. For more details see under **CONTRAINDICATIONS**.

ROACCUTANE should only be prescribed by physicians who are experienced in the use of systemic retinoids and understand the risk of teratogenicity.

Isotretinoin is teratogenic in rats and rabbits although sensitivity differs: In the rat, doses up to 50 mg/kg/day were not teratogenic but 150 mg/kg/day was teratogenic. At lower doses in the rat perinatal and post-natal studies (5, 15 and 32 mg/kg/day) increased pup mortality was noted in all treatment groups. This was attributed to a dose-related reduction in maternal food intake. Body weight development of pups was significantly impaired in the high dose groups.

In the rabbit, a dose of 10 mg/kg/day caused abortions in 9 out of 13 animals and teratogenicity and embryotoxicity were observed in the remaining 4 litters.

Use in Lactation

As isotretinoin is highly lipophilic, the passage of the drug in human milk is very likely. Because of the potential for adverse effects, breastfeeding mothers should not receive ROACCUTANE.

Use in Children

The approved therapeutic indication does not involve use in children and safety in prepubertal children has not been established. (See also PRECAUTIONS: Hyperostosis).

Interactions with Other Drugs

As a rule concomitant therapy is not indicated but non-irritant topical preparations may be used if required.

Concurrent treatment with Vitamin A must be avoided, as symptoms of hypervitaminosis A may be intensified (see ADVERSE REACTIONS).

Cases of pseudotumour cerebri and/or papilloedema have been reported in association with the use of isotretinoin. Four out of ten of these patients had retinal hemorrhages. Symptoms appeared after 21 days to 6 months therapy with 40 to 120 mg daily. Concomitant tetracycline or minocycline was administered in 5 out of 10 cases - both of these drugs have been implicated in causing intracranial hypertension. Concomitant therapy with tetracyclines is contraindicated. (See under CONTRAINDICATIONS).

Since acne is an androgen-dependent disease, contraceptives containing an androgen progestational substance, such as one derived from 19-nortestosterone (norsteroid), particularly in the presence of gynaeco-endocrinological problems, should be avoided.

The effect of microdosed progesterone preparations may be diminished by interaction with isotretinoin. Therefore, microdosed progesterone preparations or 'minipills' should not be used.

Effects on Laboratory Tests

Elevation of lipid (triglycerides and cholesterol) levels occurs with ROACCUTANE therapy. These are usually mild in doses less than 1 mg/kg/day and elevations above the normal range are unusual at 0.5 mg/kg/day. At doses above 1 mg/kg/day, elevation (above the normal range) occurs in 25% of patients.

These changes are seen more frequently in patients where a family history of lipid disorders, or obesity, alcohol abuse, diabetes mellitus or smoking is present. The changes are dose related and may be controlled by dietary means (including alcohol restriction) or dosage reduction. (See also PRECAUTIONS: Biochemical Abnormalities).

Elevated ESR values occur in about 40% of patients treated with ROACCUTANE.

A rise in aspartate aminotransferase (AST) levels may occur, especially with the higher dosages of ROACCUTANE. Although the changes have usually been within the normal range, and may return to baseline levels despite continued treatment, significant increases have occurred in a few cases, necessitating dosage reduction or discontinuation of ROACCUTANE.

Certain patients receiving ROACCUTANE have experienced problems in the control of their blood sugar. Therefore, known or suspected diabetics should have frequent blood sugar determinations performed during ROACCUTANE therapy. New cases of diabetes have been diagnosed.

A small number of patients have shown proteinuria, microscopic or gross hematuria and elevated CPK.

ROACCUTANE Product Information

ADVERSE REACTIONS

Most adverse effects appear to be dose related with the more pronounced effects occurring at doses above 1 mg/kg/day. The adverse effects may recede during continued therapy and the mucocutaneous effects were reversible with dosage reduction or discontinuation of therapy. Exacerbation of the cystic acne may occur during the initial stages of therapy.

Post-Marketing Experience

Symptoms associated with hypervitaminosis A

The most common side effects are mucocutaneous. The most frequently reported effects are dryness of the skin, in particular peeling of the palms and soles, dryness of the mucosa eg of the lips (cheilitis, which occurs in over 90% of patients), the nasal mucosa (epistaxis, which is seen in up to 30% of patients), the pharynx (hoarseness), the eyes (conjunctivitis, reversible corneal opacities and intolerance to contact lenses).

Skin and appendages disorders

Exanthema, pruritus, facial erythema/dermatitis, sweating, pyogenic granuloma, paronychia, nail dystrophy, increased formation of granulation tissue, persistent hair thinning, reversible alopecia, acne fulminans, hirsutism, hyperpigmentation, photosensitivity, photoallergic reactions, skin fragility. Acne flare occurs at the start of treatment and persists for several weeks.

Musculoskeletal system disorders

Myalgia (muscle pain) with or without elevated serum CPK values (see PRECAUTIONS), arthralgia (joint pain), hyperostosis, arthritis, calcification of ligaments and tendons and other bone changes, tendinitis.

Psychiatric and central nervous system disorders

Behavioural disorders, depression (see PRECAUTIONS), headache, increased intracranial pressure (pseudotumour cerebri), seizures.

Sensory disorders

Visual disturbances, photophobia, decreased night vision, colour vision disturbances, lenticular cataracts, keratitis, impaired hearing at certain frequencies.

Gastrointestinal system disorders

Nausea, inflammatory bowel disease such as colitis, ileitis, and hemorrhage have been reported to occur.

Patients treated with ROACCUTANE, especially those with high triglyceride levels are at risk of developing pancreatitis. Fatal pancreatitis has been rarely reported (see PRECAUTIONS).

Liver and biliary system disorders

Transitory and reversible increases in liver transaminases, some cases of hepatitis.

Respiratory System Disorders

Bronchospasm has been rarely reported; sometimes in patients with a pre-history of asthma.

Disorders of the blood

Decrease in white blood cell count, disorders of red blood cell parameters (such as decrease in red blood cell count and hematocrit), elevation of sedimentation rate increase or decrease in platelet count.

Laboratory Findings

Increase in serum triglyceride and cholesterol levels, decrease in HDL, hyperuricemia. Rare cases of elevated blood glucose have been reported, and new cases of diabetes have been diagnosed (see PRECAUTIONS).

Resistance Mechanism Disorders

Local or systemic infections due to Gram positive microorganisms (*Staphylococcus aureus*).

Miscellaneous Reactions

Decreases in hematocrit, lymphadenopathy, hematuria, and proteinuria, vasculitis (for example Wegener's granulomatosis, allergic vasculitis), allergic responses, systemic hypersensitivity, glomerulonephritis.

DOSAGE AND ADMINISTRATION

The therapeutic response to ROACCUTANE is dose related and varies between patients. This necessitates individual adjustment of dosage according to the response of the condition and the patient's tolerance of the drug. In most cases complete or near-complete suppression of acne is achieved with a 16 week course of treatment.

All patients initially should receive ROACCUTANE at doses up to 0.5 mg/kg/day bodyweight daily for a period of two to four weeks, when their responsiveness to the drug will usually be apparent. It should be noted that transient exacerbation of acne is occasionally seen during this initial period. Satisfactory initial responses have been reported from 0.05 mg/kg/day. Relapse rates on the lower doses are higher (a second course may be required in about two-thirds of patients on 0.1 mg/kg/day for 16 weeks), but there is decreased incidence and severity of adverse reactions at lower doses.

The daily dosage should be taken with food in the nearest number of whole capsules, either as a single dose or in two divided doses during the day, whichever is more convenient.

Doses up to 1 mg/kg/day may be used in patients refractory to initial treatment at lower doses.

The above daily dosages of ROACCUTANE should be continued for 16 weeks to complete the course of treatment.

After a period of two months off therapy, and if warranted by persistent severe cystic acne, a second course of therapy may be initiated.

OVERDOSAGE

Clinically, overdose has been associated with transient headache, vomiting, facial flushing, cheilosis, abdominal pain, headache, dizziness and ataxia. All symptoms quickly resolved without apparent residual effects.

The oral LD₅₀ of ROACCUTANE is greater than 4000 mg/kg in rats and mice and approximately 1960 mg/kg in rabbits.

PRESENTATION

Soft gelatin capsules

10 mg x 60 capsules, reddish-violet in colour, oval shaped, imprinted with ROA 10.

20 mg x 60 capsules, reddish-violet in colour one half, white opaque the other half, oval shaped, imprinted with ROA 20.

SPONSOR

Roche Products Pty. Limited

[name]

[name]

TGA Approved: 18 January 2001

Date of most recent amendment: 23 June 2005

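### Response is read only after outcome-triggered extra treatment, so a patient who did not respond to the assigned dose can be recorded as a responder of that arm

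*Protocol*

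**What the plan says.** The stated objective is "Comparison of the effectiveness of Roaccutane at total cumulative dosages of 120 mg/kg vs 150 mg/kg", and the hypothesis is that the higher dose is more effective both in treating acne and in producing remission.

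Three statements bear on when the outcome is read.

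- Study Duration/Visits, outcome visits: "The patients are assessed 3 months after finishing roaccutane and at one year after roaccutane treatment has ceased to record response and recurrence rates". Both visits are counted from the actual end of treatment.
- Other methods of note, item 4: "If the patient's acne is still active during the month they are due to cease treatment their course of treatment will be continued". The rule applies to both arms. It sets no limit on continuation, does not define active acne, and does not say how a continued patient is classified.
- Study Duration/Visits, on-treatment visits: "Visits include before treatment initiation, and at least every two months thereafter, including when the 120mg/kg dose and at 150mg/kg cumulative doses are reached". No outcome purpose is attached to these visits.

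Criteria for Evaluation lists lesion counts, scarring and a grade ("An acne grade will also be assigned which ranges from 1 - 8") without tying any of them to a particular visit.

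**The concern.** The trial compares two assigned cumulative doses, but the visits designated for response take place after a treatment period whose length depends on how the patient did. Acne still active at the assigned dose is the plainest sign that the dose has not worked. Under item 4 that sign leads to more drug and postpones the outcome date. If the patient then clears, the designated visit sees a clear patient, and nothing in the protocol separates that result from a response to the assigned dose.

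The direction of the bias follows from the trial's own hypothesis. If 150 mg/kg works better, more patients in the 120 mg/kg arm are continued and more of that arm's non-responders are converted. The arms are drawn together and a real difference is partly hidden. This is distinct from how far apart the received doses end up: even if continuation were capped and active acne defined, response would still be read after the extra treatment.

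**Working it through.** **The plan's own figure.** The protocol states "It has been determined that to detect a 10% difference between the two dosage schedules of Roaccutane" with 225 per group. It gives no endpoint, base rate, significance level, sidedness or power, so 225 cannot be reproduced from its own inputs. It is compatible with some assumed inputs; for example, 78% vs 88%, two-sided 5%, 80% power needs 221 per arm. The point below does not depend on how 225 was reached.

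**Inputs.** From the protocol: n = 225 per arm, and a difference of 10%, read here as 10 percentage points. Assumed, because the protocol gives no rates: a, the share not active when the assigned dose is reached; and c, the share of continued patients who later clear and stay clear to the 3-month visit. Patients not active at the assigned dose are taken to remain responders at that visit, and c is taken as equal in the two arms.

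**Recorded response.** R = a + (1 − a)c, so the recorded difference is (a150 − a120)(1 − c). Under these assumptions the difference shrinks by the factor 1 − c whatever the base rate.

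- c = 0.5: 120 arm 0.75 + 0.25 × 0.5 = 0.875; 150 arm 0.85 + 0.15 × 0.5 = 0.925; difference 5 points.
- c = 0.8: 120 arm 0.75 + 0.25 × 0.8 = 0.95; 150 arm 0.85 + 0.15 × 0.8 = 0.97; difference 2 points.

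**Power**, two-sided 5%: Φ[(d − 1.96·SE0)/SE1], where d is the difference, SE0 = √(2p̄(1 − p̄)/225), p̄ is the mean of the two rates, and SE1 = √((p1(1 − p1) + p2(1 − p2))/225).

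| Response counted | 120 vs 150 | d | SE0 | SE1 | Power |
|---|---|---|---|---|---|
| At the assigned dose | 75% vs 85% | 0.10 | 0.0377 | 0.0374 | 75.7% |
| After continuation, c = 0.5 | 87.5% vs 92.5% | 0.05 | 0.0283 | 0.0282 | 42.4% |
| After continuation, c = 0.8 | 95% vs 97% | 0.02 | 0.0185 | 0.0185 | 19.0% |

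**Other base rates.** Starting from 80% vs 90% (power 84.6%), converting 25%, 50% or 75% of the non-responders gives differences of 7.5, 5.0 and 2.5 points and power of 71%, 52% and 29%. Starting from 70% vs 80% (68.9%), the same conversions give 53%, 36% and 19%. The loss varies in size but not in direction.

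**The case against.** The strongest reply is that status at the assigned dose can be documented. Visits are required "including when the 120mg/kg dose and at 150mg/kg cumulative doses are reached", and nothing confines lesion counts or grade to the post-treatment visits. That is correct, and it rules out saying that non-response at the assigned dose goes unseen. What remains is that the protocol gives the recording of response to the post-cessation visits and gives these visits no such role.

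A reader might infer three stronger things, none of which the text supports.

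- *Every continued patient either counts as a responder or never reaches an outcome visit.* Item 4 does not say that treatment goes on until acne is no longer active. A continued patient may stop with acne remaining and be recorded as a non-responder, or clear and be recorded later as a recurrence.
- *The worst failures go missing more often in the 120 mg/kg arm.* If continuation were open-ended in both arms, patients who would never clear would be equally frequent by randomisation. If it is not open-ended, they stop and acquire an outcome date.
- *Recorded response is bound to be 100% in both arms.* At most that would describe status at finishing, under an until-clear rule the protocol does not contain. Response is recorded 3 months later.

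The share continued may also be small. Dosage and Administration says that most patients reach complete or near-complete suppression in a 16-week course. At 0.5 to 1 mg/kg/day that is 112 days × 0.5 = 56 to 112 days × 1 = 112 mg/kg, below either target. This stands as a limit on size. However, a 10-point difference in response at the assigned dose requires at least 10% of the 120 mg/kg arm to be non-responders.

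Finally, scoring rules and analysis sets may sit in an analysis plan that is not shown, so their absence is not the complaint. The outcome visit timing and the continuation rule are fixed in the protocol, and an analysis plan cannot recover an assessment that was not made at the right time.

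**Conclusion.** The point holds in this form: the designated response assessment follows outcome-triggered treatment and is dated from an end of treatment that non-response can postpone. A patient who did not respond to the assigned dose can therefore be recorded as a responder of that arm. If 150 mg/kg is the better dose and continued patients clear at similar rates in both arms, the recorded difference is too small. In the illustration, 10 points become 5 or 2, and power falls from 76% to 42% or 19%.

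Those figures rest on assumed base rates, on a common conversion share, and on no relapse before the 3-month visit. One-year recurrence is not modelled. They show how strongly the design can dilute the contrast and are not a forecast. The finding does not claim that outcomes are missing more often in one arm, nor that item 4 is clinically wrong. The change should be made because it is cheap and the result bears directly on the stated objective.

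**What to change.** Leave item 4 to the clinicians and reconcile it with the outcome timing.

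1. At the already scheduled visit at which the assigned dose is reached (120 or 150 mg/kg according to arm), and before item 4 is acted on, record lesion counts, acne grade and whether acne is active.
2. Take response to the assigned dose from that visit. Count a patient continued under item 4 as not having responded to the assigned dose, and use all randomised patients as the denominator.
3. Keep the 3-month and one-year post-cessation visits, dated as now, for sustained response and recurrence. Report there, by arm, the patients continued beyond the assigned dose.

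The 3-month and one-year clock should not be moved to the assigned-dose date. For continued patients that would place recurrence visits during or soon after treatment, when off-treatment recurrence cannot be observed properly.

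Cost: a few sentences in the protocol and no new visit. Reported response rates will be lower than those read after continuation. The classification also depends on a consistent reading of active acne, which the protocol does not define, so a working definition for recording purposes is needed at all centres.
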